## **9. SAFETY REPORTING**

### **9.1 Temporary halt for reasons of subject safety**

In accordance to section 10, subsection 4, of the WMO, the sponsor will suspend the study if there is sufficient ground that continuation of the study will jeopardise subject health or safety. The sponsor will notify the accredited METC without undue delay of a temporary halt including the reason for such an action. The study will be suspended pending a further positive decision by the accredited METC. The investigator will take care that all subjects are kept informed.

### **9.2 AEs, SAEs and SUSARs**

#### **9.2.1 Adverse events (AEs)**

Adverse events are defined as any undesirable experience occurring to a subject during the study, whether or not considered related to the intervention. All adverse events reported spontaneously by the subject or observed by the investigator or his staff will be recorded according to the Clavien-Dindo classification:

1. Grade I: Any deviation from the normal postoperative course without the need for pharmacological treatment or surgical, endoscopic or radiological interventions
2. Grade II: Requiring pharmacological treatment with drugs other than such allowed for grade I complications. Blood transfusions and total parenteral nutrition are also included.
3. Grade III: Requiring surgical, endoscopic or radiological intervention.
4. Grade IV: Life-threatening complication (including CNS complications) requiring Intensive Care management
5. Grade V: Death of a patient

The primary end points (both NRS scores for non-inferiority and LOS) of the study will be reached 30 days after surgery. We will record all AEs during the first 30 days after surgery.

#### **9.2.2 Serious adverse events (SAEs)**

A serious adverse event is any untoward medical occurrence or effect that

1. results in death;
2. is life threatening (at the time of the event);
3. requires hospitalisation or prolongation of existing inpatients' hospitalisation;
4. results in persistent or significant disability or incapacity;
5. is a congenital anomaly or birth defect; or
6. any other important medical event that did not result in any of the outcomes listed above due to medical or surgical intervention but could have been based upon appropriate judgement by the investigator.

An elective hospital admission will not be considered as a serious adverse event.

The investigator will report all SAEs to the sponsor without undue delay after obtaining knowledge of the events, except for the following SAEs (that will be listed but not reported):

1. Regular postoperative complications after VATS pleurodesis: wound infection or dehiscence, fever, bleeding, prolonged postoperative air leakage (>5 days), pneumonia, urinary tract infection, thoracic empyema, thromboembolic events and cardiac arrhythmias.
2. Complications related to the study groups (TEA and PVB): infection at the site of injection and post-puncture spinal headache.
3. In case any of those complications occur needing readmission, we will also list them but not report them.

The local investigators are responsible for reporting SAEs. All SAEs, whether or not considered to be related to the study treatment, must be reported by e-mail to

[[contact]](mailto:[contact]) within 24 hours, using the completed SAE report form.

The sponsor will report the SAEs through the web portal *ToetsingOnline* to the accredited METC that approved the protocol, within 7 days of first knowledge for SAEs that result in death or are life threatening followed by a period of maximum of 8 days to complete the initial preliminary report. All other SAEs will be reported within a period of maximum 15 days after the sponsor has first knowledge of the serious adverse events.

### **9.2.3 Suspected unexpected serious adverse reactions (SUSARs)**

Not applicable since no new medicinal products are being investigated.

### **9.3 Annual safety report**

Not applicable since no new medicinal products are being investigated.

### **9.4 Follow-up of adverse events**

All AEs will be followed until they have abated, or until a stable situation has been reached.

Depending on the event, follow up may require additional tests or medical procedures as indicated, and/or referral to the general physician or a medical specialist. SAEs need to be reported till end of the study within the Netherlands, as defined in the protocol.

### **9.5 Data Safety Monitoring Board (DSMB)**

Based on our systematic review recurrences are expected to be equal in the early and late chest tube removal. However, our patient panel emphasized that a shorter LOS (primary outcome) should not be accompanied by a higher recurrence rate in the intervention group. Therefore, a DSMB will be established to perform ongoing safety surveillance and interim analyses on the safety data. This committee is independent and has no conflict of interest with the sponsor of the study. The DSMB will monitor the safety of this study regarding

recurrence rate for early and late chest tube removal. Three interim analysis will be performed after 90, 180 and 270 patients who completed 30-day follow-up. When the incidence of recurrences after early chest tube removal exceeds the incidence after late tube removal by more than 9 cases, then early tube removal will no longer be applied and the study will continue with the two late tube removal subgroups (only randomizing and analyzing for TEA vs PVB), unless the DSMB advises otherwise. The maximum allowable skewness of 9 extra recurrences after early tube removal is based on the following considerations. First, pneumothorax is not directly life threatening and 9 recurrences extra give a modest maximum excess of 5.49% (9/164 patients in the early tube removal group). Second, a higher excess incidence ( $\geq 10$ ) leads to a decrease in expected savings in LOS by well more than 20%, and undermines the economic benefit of early tube removal too much (164 early removals save 230 hospital days and  $\geq 10$  extra recurrences reduce this gain with a least 50 days).

The advice(s) of the DSMB will only be sent to the sponsor of the study. Should the sponsor decide not to fully implement the advice of the DSMB, the sponsor will send the advice to the reviewing METC, including a note to substantiate why (part of) the advice of the DSMB will not be followed.

### **10.1 Primary study parameters**

The primary outcome of LOS (superiority) will be analyzed for the four study groups. LOS is defined as the total number of days in hospital after surgical intervention (including

readmissions within the first 30 days postoperatively). LOS will be presented in days and presented as means with standard deviation (SD) or median with interquartile range (IQR) depending on the distribution. The primary outcome regarding pain management is the mean/median proportion of pain scores  $\geq 4$  and will be presented with 95%-CI. Comparisons will be made by student's t-test or Mann-Whitney U test, respectively. Descriptive statistics will be performed for the total sample and for all four treatment groups. These will be presented in tables with regression coefficients and 95% CI for the interaction term. This allows to interpret the magnitude of any antagonism or synergism (27). To assume superiority regarding LOS, an intention-to-treat analysis will be performed. To assume non-inferiority regarding proportion of pain scores  $\geq 4$  both an intention to treat protocol and a per protocol analysis will be performed and differences will be discussed and interpreted. Multiplicity will be adjusted for to account for a type I error. Moreover, we consider an adjustment by subgroup analysis for the influence of covariates and factors expected to have important influence on the primary outcome. The multicenter setting encourages us to pay special attention to center effects and to the role of baseline characteristics on the primary outcome. Unbalanced baseline characteristics will be determined by calculating the standardized mean differences.

## 10.2 Secondary study parameters

1. QoR-15 pre-operatively as baseline score, at POD0-3 and at 4 weeks' follow up. Questionnaire scores (maximum 150 points) will be presented as means with standard deviation or median with interquartile range depending on distribution. Comparisons will be made using the student's t-test or Mann Whitney U test.
2. QoL will be measured using the EORTC QLQ-C30 at baseline and at 4 weeks, 3 months and 1 year postoperatively. Questionnaire scores will be presented as means with standard deviation or median with interquartile range depending on distribution. Comparisons will be made using the student's t-test or Mann Whitney U test.
3. The duration of having a urinary catheter will be presented in days starting from POD 0. Results will be presented as means with standard deviation or median with interquartile range depending on distribution. Comparisons will be made using the student's t-test or Mann Whitney U test.
4. Postoperative morbidity during the first 30 days according to the Clavien-Dindo classification system. Results are presented as the number of patients divided into categories (Grade I to V) according to the Clavien-Dindo classification. These proportions will be compared between the 3 randomization groups by chi square test or Fisher's exact test, based on intention to treat.
5. Total duration of postoperative chest tube drainage in days will be presented as means with standard deviation or median with interquartile range depending on

- distribution. Comparisons will be made using the student's t-test or Mann Whitney U test.
6. Postoperative pain scores at rest and during mobilization during POD 0-4 and at 4 weeks, 3 months and 1 year follow-up will be presented as means with standard deviation or median with interquartile range depending on distribution. Comparisons will be made using the student's t-test or Mann Whitney U test.
  7. Cumulative use of postoperative additional analgesics and opioids during POD 0-4 and at 4 weeks follow up will be presented in the measure of milligrams (mg) using means with standard deviation or median with interquartile range depending on distribution. Comparisons will be made using the student's t-test or Mann Whitney U test.
  8. The degree of mobility defined as an ordinal scale (in bed (1), in the chair (2), to the toilet (3), outside the patient's hospital room (4)) and will be presented as the number of patients per category for POD 0-4. Comparison between the three randomization groups will be made using the Chi square test or Fisher's exact test.
  9. Health status scored by the EQ-5D tool at baseline, POD 0-3, after 4 weeks, 3 months and 1 year follow-up. Questionnaire scores will be presented as means with standard deviation or median with interquartile range depending on distribution. Comparisons will be made using the student's t-test or Mann Whitney U test.
  10. Patient satisfaction using the 5-point Likert scale (not at all satisfied, slightly satisfied, neutral, very satisfied and extremely satisfied) will be presented as the number of patients per category for POD 0-4. Comparisons between the three randomization groups will be made using the Chi square test or Fisher's exact test.
  11. Cumulative use of additional chest X-rays and/or CT-scans will be documented including reasons. Evaluation of the reasons of additional use will take place using descriptive statistics. Also, the amount of additional imaging will be compared between the three randomization groups using the Chi square test or Fisher's exact test.
  12. A cost effectiveness and cost-utility analysis from a health care and societal perspective of both chest tube drainage and analgesic techniques will be performed. The time horizon is 1 year, the period it takes to resolve the aftermath of a pneumothorax (and possible recurrence) in this mostly young and healthy population. Whereas safety margins regarding recurrence (interim analyses by our DSMB) as well as upper margins for non-inferiority regarding pain are in place, we expect that the reduction in LOS and improved QoR during the POD 0-3 generate the economic benefits. Hence, cost-effectiveness and cost-utility analyses are done with total costs, out-of-hospital days during follow-up, total QoR score and QALYs. Incremental ratios

are calculated for the extra costs per additional day out of hospital, per unit increase in QoR score point and per additional QALY. Sensitivity analyses are done to account for sampling variability (following bootstrapping) and plausible ranges in unit costs of surgical and anaesthesiologic treatments. Cost-effectiveness acceptability curves are drawn, showing the probability of early chest tube removal or single-shot PVB sedation being cost-effective at various levels of willingness-to-pay per QALY up to 50,000 euros. Subgroup analyses are done for patients treated by pleurectomy or chemical pleurodesis and for patients above or below under 40 years of age. Regarding cost analysis, the evaluation includes health care, patient/family, and other costs. Health care costs include the costs of all analgesic procedures, therapeutic (repeat) interventions, medication, admissions, day care treatments, specialist consultations, and out-of-hospital care (like general physician, physiotherapy etc.). Out-of-pocket expenses include the costs of health-related travel, over-the-counter medication, informal help, etc. Other costs like productivity losses reflect costs of sick leave from work or lowered efficiency while at work. Data on resource use are gathered with clinical report forms, hospital information systems, and patient questionnaires. Patients complete the DMCQ and PCQ, adjusted to the study setting and extended, at POD 30, 3 months and 1 year after surgery. Micro-costing (general anesthesia, surgical and anaesthesiologic equipment, procedure duration, involved personnel, and overhead) is done in participating centers to derive real unit costs of the index interventions. The most recent Dutch manual on costing in health care or passer-by tariffs are applied to other health care resources. The friction costs method is applied to derive the costs of lost productivity. Out-of-pocket expenses are based on self-report. After price-indexing all costs will be expressed in Euros with base-year 2026.

13. With a budget impact analysis, the impact on the national health care budget will be assessed. Single shot PVB instead of epidural analgesics during surgery for PSP and supervised earlier postoperative chest tube removal will have financial consequences for the budget of medical specialist hospital care, from governmental, insurer and provider perspectives. The planning horizon of the budget impact analysis will be the first 4 full calendar years following study closure. The historical trend in yearly numbers of (adult) pneumothorax cases extracted from e.g. [www.opendisdata.nl](http://www.opendisdata.nl) will statistically be curve-fitted conservatively to allow realistic forecasting of future yearly case counts for the planning horizon. Linkage of the expected incidence of PSP with the trial-based differences in specialist medical care costs between the most efficient alternative treatment strategy and the standard strategy of epidural analgesics plus late chest tube removal will enable the analysis of the potential budget impact. The

budget impact analysis will be incidence-based, because most treatment costs during the first year following spontaneous pneumothorax will be made within months following the actual incident. Hence, all expected costs of medical care during the first year of patients' follow-up will be attributed to the calendar year when the incident is expected to occur. National implementation scenarios will be discussed among professional societies and our involved implementation expert during the final year of the study period in order to target the most feasible (increase in) yearly diffusion rate of the most efficient alternative during the planning horizon. An alternative impact scenario will be run based on reimbursements rather than real unit costs for the projected use of hospital care. Budget impacts will be expressed in millions of Euros and the assessment will comply with the most recent ISPOR good practice guideline for budget impact analysis at the time of reporting.

### **10.3 Other study parameters**

An additional subgroup analysis will be performed regarding age  $\geq$  and  $<$  40 years and between the two different surgical techniques (e.g. chemical or mechanical pleurodesis), since age and type of pleurodesis might have an influence on recurrence rate and/or LOS. Known history of pulmonary emphysema and presence of pre-existent bullae on preoperative chest CT-scan will be documented and will be checked for being a confounder for recurrence rate and/or LOS.

During the insertion of a chest tube the Thopaz+ system register the amount of air leak and fluid production per patient. After removal of the chest tube these Thopaz data will be extracted from the Thopaz+ system and the course of the amount of air leak and fluid production during postoperative drainage will be evaluated. Outcomes will be presented as means with SD or median with IQR depending on the distribution. Comparisons will be made by student's t-test or Mann-Whitney U test, respectively. Descriptive statistics will be performed for the total sample and for all four treatment groups. These will be presented in tables with regression coefficients and 95% CI for the interaction term.

#### *Patient participation (Patient preference study)*

During the preparation of this proposal our patient advisory board was consulted. During multiple meetings they actively participated in designing the first draft of the patient information folder and reviewing the study protocol. They are also involved in a patient preference study on preferred pain management and chest tube management. For this patient preference study, structured questionnaires were made in collaboration with dr [name] from the Medical Decision Making department at the Leiden University Medical Centre with vast experience in patient preference models.

**10.4 Interim analysis**

During the study period 3 interim analysis will be performed under supervision of a DSMB (see *chapter 9.5 Data Safety Monitoring Board*). The interim analysis will take place after 90, 180 and 270 patients who completed 30-day follow-up. In the intervention group (early tube removal) and the control group (late tube removal) the amount of early recurrences will be assessed. In case the intervention group exceeds the maximum allowable skewness of 9 extra recurrences, the early tube removal group will be stopped. The definition for a recurrence is an ipsilateral recurrence confirmed by X-ray or CT-scan and requires any kind of treatment.

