The shortened LOS however is only acceptable in case recurrence rates are equal between the early and late chest tube removal groups (patients' perspective). Therefore, three interim analyses will be performed under supervision of a DSMB after 90, 180 and 270 patients who completed 30-day follow-up. When the incidence of recurrences after early chest tube removal exceeds the incidence after late tube removal by more than 9 cases, then early tube removal will no longer be applied and the study will continue with the two late tube removal subgroups, unless the DSMB advises otherwise. The maximum allowable skewness of 9 extra recurrences after early tube removal is based on the following considerations. First, pneumothorax is not directly life threatening and 9 recurrences extra give a modest maximum excess of 5.49% (9/164). Second, a higher excess incidence ( $\geq 10$ ) leads to a decrease in expected savings in LOS by well more than 20%, and undermines the economic benefit of early tube removal too much (164 early removals save 230 hospital days and  $\geq 10$  extra recurrences reduce this gain with a least 50 days).

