## 8. METHODS

### 8.1 Study parameters/endpoints

#### 8.1.1 Main study parameter/endpoint

As explained in the sample size section, we discussed the relevance and importance of several outcome measure with a patient panel. Although we expect the largest advantage of our interventions to be a shortened LOS with high impact on cost-effectiveness, the patient panel emphasized that short LOS is important but inferior to recurrence rate of pneumothorax. Next to recurrence rate, patients indicated acute postoperative pain to be an important topic as well. Lastly, patients emphasized uniformity in chest tube policy, the necessity of having a bladder catheter and uniformity in radiology assessments as important factors as well. Together with the patient panel we made the following ranking: 1) recurrence rate; 2) postoperative acute pain; 3) LOS; 4) uniformity in chest tube policy; 5) the need for a urinary catheter; and 6) uniformity in radiologic assessments (CT and X-ray). In addition, the reference panel of Patiëntenfederatie Nederland advised us during the subsidy application to include QoL as outcome parameter in our study.

Primary outcomes:

1. Safety outcome: absolute number of patients with recurrence (maximum allowable difference between early and late chest tube removal groups of 9 recurrences) defined as having an ipsilateral recurrent pneumothorax after chest tube removal, confirmed by X-ray or CT within 1-year, requiring reintervention (either tube thoracostomy or reoperation) or hospital readmission.
2. The primary outcome measure (non-inferiority) for our second intervention (single-shot PVB) will be the proportion of NRS  $\geq 4$ , defined as the number of NRS scores  $\geq 4$  divided by the total number of NRS measurements obtained during POD 0-3. A minimum of 11 NRS pain scores will be collected (1 at the recovery room, and 10 afterwards on the ward).
3. The primary outcome measure for our both interventions (early chest tube removal and single-shot PVB) will be LOS, defined as the total number of in-hospital days including readmissions due to complications or recurrence within 30 postoperative days. The day of surgery will be POD 0. Discharge criteria are: absence of chest tube, sufficient pain control (NRS $<4$ ) with oral pain medication, absence of fever ( $< 38.5$  °C) and being able of self-care.

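### The limit of more than 9 extra recurrences is set for the full 164 early-removal patients and the 1-year outcome, but is applied unchanged at three partial, 30-day looks under a different recurrence definition

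*Protocol*

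**What the plan says.** Sections 4.4, 8.8, 9.5 and 10.4 give one numerical rule for the chest-tube comparison. Early removal is discontinued when its recurrence count "exceeds the incidence after late tube removal by more than 9 cases", unless the DSMB advises differently. On timing, section 9.5 states: "Three interim analysis will be performed after 90, 180 and 270 patients who completed 30-day follow-up". Section 10.4 repeats the schedule and says that at these looks "the amount of early recurrences will be assessed". It then gives the consequence without any adjustment by look: "In case the intervention group exceeds the maximum allowable skewness of 9 extra recurrences, the early tube removal group will be stopped".

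The number 9 has two justifications, both at full group size. The first is that "9 recurrences extra give a modest maximum excess of 5.49% (9/164 patients in the early tube removal group"). The second is economic: 164 early removals are expected to save 230 hospital days, and 10 or more extra recurrences would use up at least 50 of them.

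Section 8.1.1 uses the same maximum difference of 9 for the primary safety outcome, defined there as an ipsilateral recurrence after tube removal, "confirmed by X-ray or CT within 1-year, requiring reintervention (either tube thoracostomy or reoperation) or hospital readmission". Section 10.4 defines it differently for the interim looks: "The definition for a recurrence is an ipsilateral recurrence confirmed by X-ray or CT-scan and requires any kind of treatment".

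**The concern.** A limit expressed as a share of 164 patients over a year is being used as a fixed count on a fraction of those patients, after a month of follow-up. The fewer patients evaluated, the larger the excess rate that the rule tolerates, so it is least sensitive when stopping would spare most patients.

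The patient panel ranked recurrence first (section 8.1.1), and section 11.4 names the DSMB as the safeguard because a higher rate would not be acceptable. If look 1 passes without a crossing, sponsor and sites may read this as evidence that the excess is below 5.49%, which it cannot be.

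The two definitions add to this: the same 9 cases limit two different outcomes.

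**Working it through.** **Inputs.** Limit: more than 9 extra, that is a difference of at least 10 (4.4, 8.8, 9.5, 10.4). Looks: 90, 180 and 270 patients (9.5, 10.4). Allocation 1:1:1:1 (8.2.1), so about 45, 90 and 135 patients per tube group. Full size: 164 per tube group (4.4). Late-removal recurrence from the systematic review: 5.57% (5.3); no follow-up period is given for it. The protocol gives no 30-day recurrence risk and no share of 1-year recurrences that occur by day 30. I assume a 30-day late-group risk between 1% and 5.57% and vary the share.

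**The plan's own figures reproduce.** 9/164 = 5.49%. 164 × 1.4 days = 229.6, stated as 230. 50/230 = 21.7%, in line with the stated loss of more than 20%.

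**Observed excess needed to cross.**

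| Look | Early-removal patients | Share of the 328 | Excess needed | Relative to 5.49% |
|---|---|---|---|---|
| 1 | 45 | 90/328 = 27% | 10/45 = 22.2% | 4.0 |
| 2 | 90 | 180/328 = 55% | 10/90 = 11.1% | 2.0 |
| 3 | 135 | 270/328 = 82% | 10/135 = 7.4% | 1.3 |

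**Chance of crossing.** Each look adds 45 patients per group. With E and L the cumulative early and late counts, both binomial, the rule crosses at the first look where E − L ≥ 10. Cumulative probabilities, with the range over a late-group 30-day risk of 1% to 5.57% and the whole excess visible by day 30:

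| True excess | Look 1 | By look 2 | By look 3 |
|---|---|---|---|
| 0 | 0% | at most 0.1% | at most 0.6% |
| 5.49 points | at most 0.5% | 4–11% | 24–33% |
| 10 points | 2–4% | 42–45% | 79–86% |
| 16.5 points (three times the limit) | 21–25% | 88–93% | 99% or more |

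**If part of the recurrences comes after day 30.** Take 5.57% as the late group's 1-year risk and a true 1-year excess of 11 points, twice the limit. With every recurrence seen by day 30, the cumulative chances are 6%, 54% and 86%. With half seen by then they are 0.1%, 7% and 29%. With a quarter they are below 0.1%, 0.2% and 2%.

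**Plain scaling, as an illustration.** 9/164 of 45, 90 and 135 is 2.5, 4.9 and 7.4 cases, so crossing would occur at 3, 5 and 8. With a true 10-point excess visible by day 30, the cumulative chances are 76–82%, 90–95% and 94–98%. With no true difference, this rule would cross at some look in about 1% of trials (late risk 1%) to 15% (late risk 5.57%; 12% at look 1 alone).

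**Definitions side by side.** Section 8.1.1 requires tube thoracostomy, reoperation or readmission, after tube removal and within 1 year. Section 10.4 requires treatment of any kind and states neither a time limit nor that the tube has been removed. Section 10.4 is mostly the broader of the two, but a readmission for observation without treatment would count under 8.1.1 and not under 10.4.

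**The case against.** The strongest defence is that a fixed count is deliberate. Section 8.1.1 words the outcome as an absolute number of patients, and the economic argument can be read as a budget of extra recurrences for the whole trial. Stopping once that budget is exceeded is coherent, and a boundary that is strict early and looser later is a familiar monitoring shape. This stands in part, but both justifications are computed on 164 early removals, and one is an explicit percentage that the rule does not apply at any look.

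A second defence is that 5.49 points is the tolerated excess, so rare crossing at that value is no failure. That is right: even with all 164 per group, a true 5.49-point excess gives a difference of 10 or more only about 43–46% of the time. The case therefore rests on excesses well above the limit.

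Three stronger readings are tempting but not supported:

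- *The rule can hardly trigger at any early look.* This holds firmly only at look 1. At look 2, a 10-point excess visible by day 30 crosses in 42–45% of trials. Lower figures depend on a day-30 share that the protocol does not give.
- *The rule is the only protection.* Section 9.5 gives the DSMB ongoing surveillance and the discretion to depart from the rule. Section 9.2.2 has serious adverse events reported within 24 hours and does not name recurrence among the exempt complications. Section 9.1 requires suspension if safety is jeopardised. It is the only numerical rule.
- *Recurrences after day 30 are expressly excluded.* In sections 4.4 and 9.5 the 30-day follow-up sets the timing of the looks. Only section 10.4 restricts the count to early recurrences, without defining the term. Exclusion is its natural reading, but it is not stated.

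**Conclusion.** The point holds, as something that should be fixed. The written rule does not enforce its own 5.49% at any look, because it needs observed excesses of 22.2, 11.1 and 7.4 points. Look 1 gives almost no protection: even an excess of three times the limit, fully visible by day 30, crosses in only 21–25% of trials. Looks 2 and 3 have real but weaker power, which falls steeply if recurrences come late.

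The required excesses need only the protocol's figures and equal allocation. The probabilities also rest on the assumed 30-day late-group risk of 1% to 5.57%, on independent binomial counts, and on the assumed share seen by day 30. The figure 9/164 is correct; the fault is its use at partial samples and a shorter horizon. The conflict between the definitions in 8.1.1 and 10.4 is plain but secondary, since the interim wording is mostly broader and explains little of the low sensitivity.

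**What to change.** Reconcile sections 4.4, 8.1.1, 8.8, 9.5 and 10.4 on three points:

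1. Use one recurrence definition throughout, that of section 8.1.1.
2. Count all recurrences known at each data cut-off, and show 30-day counts alongside.
3. State the limit relative to the number of early-removal patients evaluated at each look, and stop presenting the full-sample count as a 5.49% limit.

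The sponsor and DSMB should choose the look-specific limits from their operating characteristics and record these in the DSMB charter. The DSMB's discretion stays. The scaled counts of 3, 5 and 8 are an illustration, not a proposal. They would stop early removal in about 1–15% of trials with no true difference, and in about 68–69% at the tolerated 5.49 points. They would also still apply a 1-year proportion to incomplete follow-up.

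The cost is wording in five sections and the charter. No new data are needed, because the 4-week visit and the 3- and 12-month calls already collect recurrences. The real price is that any limit more sensitive at the early looks stops early removal more often by chance, which would end the chest-tube comparison, including its length-of-stay endpoint. The change is useful only if made before the looks take place.
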